6.3.1.1 Graphical presentation of results

The mean (+/- SE) and mean change from baseline plots for total number of colony forming units, all spirometry parameters (FEV1, FVC and FEV1/FVC ratio) and HRCT parameters including regional and global air tapping changes will be presented by treatment. Plot for the estimated treatment differences and associated 80% confidence intervals for change from baseline in total number of colony forming units, all spirometry parameters and HRCT parameters including regional and global air tapping changes.

6.4 Exploratory objectives

Commercially Confidential Information

6.4.2 Descriptive analyses

Commercially Confidential Information

7 Statistical methods for safety and tolerability data

For all safety analyses, the safety set will be used. All listings and tables will be presented by treatment group.

Safety summaries (tables, figures) include only data from the on-treatment period with the exception of baseline data which will also be summarized where appropriate (e.g. change from baseline summaries). In addition, a separate summary for death including on treatment and post treatment deaths will be provided. In particular, summary tables for adverse events (AEs) will summarize only on-treatment events, with a start date during the on-treatment period (treatment-emergent AEs).

7.1 Variables

Adverse events, vital signs (blood pressure, pulse rate, body temperature), ECG intervals, laboratory measurements, as well as subject demographics, baseline characteristics, and treatment information.

7.2 Descriptive analyses

Categorical data will be presented as frequencies and percentages. For continuous data, mean, standard deviation, median, minimum, and maximum will be presented.

Subject demographics and other baseline characteristics

All data for background and demographic variables will be listed by treatment group and subject. Summary statistics will be provided by treatment group for the Safety analysis set.

Other screening/baseline characteristics will be summarized including:

- Smoking Status
- HRCT
- Spirometry (Absolute and percent predicted values of FEV1, FVC)
- hsCRP
- Fibrinogen plasma concentration
- COPD Assessment Test (CAT)
- Sputum bacterial load

Relevant medical histories and current medical conditions at baseline will be summarized by system organ class and preferred term, by treatment group.

Subject disposition

A disposition summary will be presented for all subjects. This table will present the number and percentage of subjects who completed each study epoch and discontinued early for each epoch, along with the reasons for early discontinuation.

The number and percentage of subjects in each analysis set will be summarized for all subjects. All analysis set results will be presented in listings by treatment group and subject. A separate listing of all subjects excluded from any analysis set and the reasons for their exclusion will be provided.

All study epoch completion data will be listed by treatment group and subject.

Treatment

Data for study drug administration, rescue medication and concomitant therapies will be listed by treatment group and subject.

Summary statistics will be provided for the duration of exposure to study treatment using the safety analysis set.

Novartis	Confidential	Page 18 of 20			
SAP Amendment 1		Study No. CQBW251B2202			
Concomitant medications and significant non-drug therapies prior to and after the start of the					

Concomitant medications and significant non-drug therapies prior to and after the start of the study treatment will be listed and summarized according to the Anatomical Therapeutic Chemical (ATC) classification system, by treatment group.

Vital signs

All vital signs data will be listed by treatment group, subject, and visit/time and if ranges are available, abnormalities (and relevant orthostatic changes) will be flagged. Summary statistics will be provided by treatment and visit/time.

ECG evaluations

All ECG data will be listed by treatment group, subject and visit/time, abnormalities will be flagged. Summary statistics will be provided by treatment and visit/time.

Clinical laboratory evaluations

All laboratory data will be listed by treatment group, subject, and visit/time and if normal ranges are available, abnormalities will be flagged. A separate listing is provided presenting all parameters in a subject with any abnormal values. Summary statistics will be provided by treatment and visit/time. Shift tables using the low/normal/high (low and high) classification will be used to compare baseline to the worst on-treatment value.

Adverse events

All information obtained on adverse events will be displayed by treatment group and subject.

Summary tables for adverse events (AEs) will summarize only on-treatment events, with a start date during the on-treatment period (treatment-emergent AEs).

The on-treatment period lasts from the date of first administration of study treatment to 1 week after the last actual administration of any study treatment.

The number (and percentage) of subjects with treatment emergent adverse events (events started after the first dose of study medication or events present prior to start of double-blind treatment but increased in severity based on preferred term) will be summarized in the following ways:

- by treatment, primary system organ class and preferred term.
- by treatment, primary system organ class, preferred term and maximum severity.
- by treatment, Standardized MedDRA Query (SMQ) and preferred term.

Separate summaries will be provided for study medication related adverse events, death, serious adverse events, other significant adverse events leading to discontinuation.

A subject with multiple adverse events within a primary system organ class is only counted once towards the total of the primary system organ class.

Listings will be provided for all AEs, SAEs and fatal AEs.

Novartis	Confidential	Page 19 of 20
SAP Amendment 1		Study No. CQBW251B2202

For the legal requirements of ClinicalTrials.gov and EudraCT, two required tables on treatment emergent adverse events which are not serious adverse events with an incidence greater than 5% and on-treatment emergent serious adverse events and SAE suspected to be related to study treatment will be provided by system organ class and preferred term on the safety set population.

If for an individual subject, several consecutive AEs (irrespective of study treatment causality, seriousness and severity) occurred with the same SOC and PT:

- a single occurrence will be counted if there is ≤ 1 day gap between the end date of the preceding AE and the start date of the consecutive AE
- more than one occurrence will be counted if there is > 1 day gap between the end date of the preceding AE and the start date of the consecutive AE.

For occurrence, the presence of at least one SAE / SAE suspected to be related to study treatment / non-SAE has to be checked in a block e.g., among AE's in $a \le 1$ day gap block, if at least one SAE is occurring, then one occurrence is calculated for that SAE.

The number of deaths resulting from SAEs suspected to be related to study treatment and SAEs irrespective of study treatment relationship will be provided by SOC and PT.

Confidential

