## Treatment period (from Day 1 to Day 84)

Once eligibility has been confirmed from Screening and Baseline assessments, subjects will be randomized in 1:1 ratio into one of the two treatment arms; placebo b.i.d. or QBW251 300 mg b.i.d.

The treatment period is 84 days in duration, with dosing twice daily. During this period, subjects will have to return to the site at Day 28, Day 56 and Day 84 for CCI blood/sputum sample collections, PK, safety, efficacy assessments, and eDiary check. At these visits, subjects will return all used and unused study medication and packaging. At Day 14, the site will call the subject to evaluate compliance and to check subject's wellbeing.

Pharmacokinetic blood sampling (pre and post-dose) will be done at Day 1, Day 28, Day 56 and Day 84 visits. Additionally, a subset of approximately 30-40 subjects will undergo pharmacokinetic serial sampling pre and up to 8 hours post-dose on Day 1 and on Day 28.

As a formal thorough QT assessment of QBW251 has not been completed, triplicate ECGs preand post-dose at Tmax will be performed at visits on Day 1, Day 28, Day 56 and Day 84 (end of treatment). These assessments will be complemented by PK sampling (trough and Cmax) on the matching time-points, at visits on Day 1, Day 28, Day 56 and Day 84.

A second HRCT will be performed at Day 84 after the morning dose of study medication at site. If the HRCT can't be performed at Day 84 for any reason, the exam needs to be planned within the 3 coming days and subject must continue to take study medication.

Subjects experiencing an exacerbation during the treatment period will continue with the study treatment along with the standard of care (SOC) therapy for a moderate exacerbation (i.e. antibiotic and/or systemic corticosteroids). Prior to the SOC therapy administration, subjects have to visit their study center for sputum sample collection in order to determine if there are changes in pathogen or bacterial load which may have resulted in the exacerbation.

Subjects with a severe exacerbation who need to be treated in the hospital will be discontinued of study treatment during this time with the possibility to restart study treatment 2 weeks after the last SOC therapy intake for the exacerbation.

End of treatment assessments will be performed at Day 84 visit.

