### 6.5.1.2 QTcF prolongation

In case of QTcF > 500 msec (or QTcF prolongation > 60 msec from baseline/Day 1):

- Assess the quality of the ECG recording and the QT value and repeat, if needed
- Interrupt study investigational treatment
- Determine the serum electrolyte levels (in particular for hypokalemia, hypomagnesemia). If abnormal, correct abnormalities.
- Consider collecting a time-matched PK sample on that visit (if not already scheduled per Table 8-1) and record time and date of last study treatment intake.
- If QTcF confirmed by the Central Reading > 500 msec:

- Permanently discontinue the study treatment (see Section 9.1).
- Take a blood sample for PK analysis. Timepoint should be as close as possible to the ECG recording in question
- Consult with a cardiologist (or qualified specialist)
- Increase cardiac monitoring as indicated, until the QTcF returns to ≤ 480 msec
- Review concomitant medication use for other causes for QT prolongation (refer to http://www.qtdrugs.org for known QT prolonging drugs), and for drugs with the potential to increase the risk of drug exposure related QT prolongation
- Check the dosing schedule and treatment compliance

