# 9 Study discontinuation and completion

#### 9.1 **Discontinuation**

## 9.1.1 **Discontinuation of study treatment**

Discontinuation of study treatment for a subject occurs when study treatment is stopped earlier than the protocol planned duration, and can be initiated by either the subject or the investigator.

The investigator must discontinue study treatment for a given subject if, he/she believes that continuation would negatively impact the subject's well-being.

Study treatment must be permanently discontinued for a subject under the following circumstances:

- Subject/guardian decision
- Pregnancy
- Use of prohibited treatment as per recommendations in the prohibited treatment Section 6.2.2
- Any situation in which study participation might result in a safety risk to the subject (e.g. hospitalization)
- Following emergency unblinding

or

- Emergence of AE reported as severe and suspected to be related to investigational drug or an SAE reported and suspected to be related to investigational drug
- Emergence of an SAE not suspected to be related to investigational drug in a subject with a verified exposure above the threshold AUC0-24h≥91,700 ng\*h/ml. The investigator must permanently discontinue the investigational study drug as soon as possible upon receipt of the PK results.
- A subject with a verified exposure above the upper range of the individual animal (monkey) model exposure (AUC0-24h≥159,000 ng\*h/ml). The investigator must stop study drug as soon as possible upon receipt of the PK results.
- Any laboratory abnormalities that in the judgment of the investigator, taking into consideration the subject's overall status, prevents the subject from continuing participation in the study
- Any liver event requiring immediate discontinuation of study treatment, as specified in Table 16-2
- Individual serum creatinine increase  $\geq 50\%$  compared to baseline (must be confirmed). Confirmation of the assessment should be made as quickly as possible after an abnormal result is received. A renal event leading to subject discontinuation should be followed up until event resolution (Serum Cr within 10% of baseline), or event stabilization (Serum Creatinine level within  $\pm 10\%$  variability over last 6 months)
- Study drug can be temporarily interrupted as a response to the occurrence of adverse events that do not fulfill the requirements above described for permanent discontinuation (refer to Section 6.5.1).

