# 16 Appendices

# 16.1 Appendix 1: Clinically notable laboratory values and vital signs

The central laboratory will flag laboratory values falling outside of the normal ranges on the central laboratory reports. Investigators are responsible for reviewing these abnormal values for clinical significance, signing the laboratory reports to indicate their review, and reporting values considered clinically significant in the appropriate eCRF.

Any clinically significant abnormal laboratory value should be evaluated and followed-up by the investigator until normal or a cause for the abnormality is determined.

See Section 16.2 for specific liver event and laboratory test trigger definitions and follow-up requirements.

For ECGs, a notable QTc value is defined as a QTcF (Fridericia) interval of  $\geq$  450 msec for males or  $\geq$  460 msec for females – all such ECGs will be flagged by the Central ECG reading and require assessment for clinical relevance and continuance of the subject by the Investigator.

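### The SAP has no by-arm count of subjects meeting the protocol's own QTcF, creatinine and liver criteria, and the change-from-baseline criteria can be met without any flag or shift

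*SAP*

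**What the plan says.** **Planned outputs (SAP 7.2).** For ECGs: "All ECG data will be listed by treatment group, subject and visit/time, abnormalities will be flagged", plus summary statistics by treatment and visit or time. For laboratory data: "if normal ranges are available, abnormalities will be flagged", plus a listing of all parameters for any subject with an abnormal value, summary statistics, and "Shift tables using the low/normal/high (low and high) classification will be used to compare baseline to the worst on-treatment value". Continuous data are summarised by mean, SD, median, minimum and maximum. The introduction to SAP section 7 restricts safety summaries to the on-treatment period, except for "baseline data which will also be summarized where appropriate (e.g. change from baseline summaries").

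**Protocol criteria.**
- QTcF, section 6.5.1.2: treatment is interrupted "In case of QTcF > 500 msec (or QTcF prolongation > 60 msec from baseline/Day 1"). It is permanently discontinued if central reading confirms a value above 500 ms.
- QTcF, Appendix 16.1: "a notable QTc value is defined as a QTcF (Fridericia) interval of" at least 450 ms in men or 460 ms in women.
- Creatinine, section 9.1.1: permanent discontinuation for an increase of at least 50% "compared to baseline (must be confirmed"). Table 16-3 sets actions for a confirmed 25-49% increase and for a 50% increase.
- Liver, Tables 16-1 and 16-2: categories by multiples of ULN, such as ALT or AST above 3, 5 and 8 x ULN.

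**Reason for the ECG schedule.** Section 3.1 explains: "As a formal thorough QT assessment of QBW251 has not been completed, triplicate ECGs" are taken before and after dosing on Days 1, 28, 56 and 84.

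**The concern.** Safety and tolerability is a stated objective, with ECG intervals and laboratory evaluations as endpoints. The protocol collects intensive ECG data because the QT effect is not yet characterised, and it sets explicit limits at which treatment is interrupted or stopped. The natural safety question is how many subjects in each arm reached those limits. No visible output answers it.

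The scales also differ. Normal-range flags and shift classes compare a value with a fixed limit. The QTcF rise and both creatinine limits compare a value with the subject's own baseline. A subject can therefore meet an interruption criterion (QTcF) or a stopping criterion (creatinine) while the flag column is empty and the shift table shows normal to normal. QT and renal effects may appear as a few subjects with large changes, which is what a threshold count shows and a fixed-limit class may not.

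**Working it through.** The plan gives no figure to reproduce here; the check compares thresholds.

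**1. QTcF rise above 60 ms.** The SAP gives no ECG flag limit, so take the notable limit of Appendix 16.1. A rise just over 60 ms stays unflagged if baseline + 60 is below the limit:
- men: 450 - 60 = 390, so baselines below 390 ms;
- women: 460 - 60 = 400, so baselines below 400 ms.

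In whole milliseconds with a rise of 61, the highest such baselines are 388 and 398 ms. The entry criteria set a ceiling (450 and 460 ms) and no floor, so these baselines are eligible. Examples: a man going from 380 to 445 ms (+65) and a woman going from 390 to 455 ms (+65) both meet the interruption criterion, and neither reaches the notable limit.

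**2. QTcF above 500 ms.** 500 exceeds both 450 and 460, so this criterion cannot be met below the notable limit.

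**3. Creatinine.** A rise by fraction r stays in range if baseline x (1 + r) is at or below ULN:
- 50% rise: 1/1.5 = 0.67, so baselines at or below 0.67 x ULN;
- 25% rise: 1/1.25 = 0.80, so baselines at or below 0.80 x ULN.

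Example: 0.70 to 1.05 mg/dL is +50% and normal to normal if ULN is at least 1.05 mg/dL (assumed; the documents give no ULN).

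**4. Liver.** Every criterion expressed as a multiple of ULN lies above ULN, so it is flagged and classed high. But ALT at 1.1 x ULN and at 9 x ULN fall in the same class, so the shift table cannot separate the categories of Tables 16-1 and 16-2.

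**5. Summary statistics.** One subject at +65 ms moves an arm mean by 65/50 = 1.30 ms with 50 subjects, or 65/42 = 1.55 ms with 42 (half of the planned 100 randomized and of the expected 84 completers). A maximum of absolute QTcF need not help: 445 ms is below the entry ceiling, and another subject may have a higher value. A maximum change from baseline would show +65 ms, but not how many subjects passed 60 ms.

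**6. How many subjects start low enough (assumption only).** The documents give no QTcF distribution. With a normal baseline, mean 400-420 ms and SD 15-25 ms, and ignoring the entry ceilings, about 2-33% of men are below 389 ms and 8-48% of women below 399 ms. These are shares with a low baseline, not risks of an unflagged event, which also needs the rise.

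**The case against.** The plan has other routes to a signal. All ECG and laboratory values are listed. Minimum and maximum are planned, and change-from-baseline summaries are foreseen where appropriate. Clinically significant ECG abnormalities are to be reported as adverse events (protocol 8.4.2), review of laboratory values includes significant changes from baseline (10.1.1), and most liver rows of Table 16-2 require an AE record. AEs are tabulated by arm, and early discontinuations are tabulated with reasons. The study is descriptive and non-confirmatory, and SAP 1.4 records a decision to stop it before completion.

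Much of this stands, and several stronger readings fail:
- A reader might infer that all the protocol's stopping criteria can be hidden. They cannot: QTcF above 500 ms, the only QTcF limit for permanent discontinuation, and the liver multiples always exceed the fixed limits.
- A reader might infer that the SAP prescribes 450/460 ms flags. It says only that abnormalities are flagged; the limit is taken from Appendix 16.1, and the SAP does not exclude flagging a 60 ms rise.
- A reader might infer that repeat or unscheduled ECGs drop out. The SAP summarises by visit or time and lists all ECG data; nothing limits it to scheduled visits.
- A reader might infer that the tables would show no signal. The routes above may reveal individual cases.

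None of these routes is a count by arm. AE reporting of an ECG or laboratory finding generally depends on judged clinical significance, symptoms or need for therapy. A temporary QTcF interruption is not an early discontinuation. Drug administration is only listed, and the change-from-baseline summaries are not tied to QTcF or to percent creatinine change.

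**Conclusion.** The concern holds in a limited form. The visible SAP gives no by-arm count of subjects meeting the protocol's QTcF, creatinine or liver criteria. Two kinds of criterion can also be met unseen in the flags and shift tables: a QTcF rise above 60 ms from baselines below 390 ms (men) or 400 ms (women), and creatinine rises of 50% and 25% from baselines at or below 0.67 and 0.80 x ULN. For the liver criteria the fault is a class that is too coarse, not concealment.

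The creatinine result is pure arithmetic. The QTcF result assumes that flags follow Appendix 16.1. The number of subjects affected cannot be derived from the documents. The DMC section and the dose modification details are blacked out, so further outputs may exist there. This is a cheap reporting improvement that serves the stated safety objective; it does not show that a safety signal would be missed.

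**What to change.** Add to SAP 7.2 a table giving, per arm, the number and percent of subjects who meet each of these limits at any on-treatment time, unscheduled assessments included:
- QTcF above 500 ms, and QTcF increase above 60 ms from baseline;
- creatinine increase of 25-49% and of at least 50% from baseline, with confirmed cases shown separately;
- the liver categories of Table 16-1, with the 8 x ULN level of Table 16-2.

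Flag the same criteria in the listings. State that the mean of each ECG triplicate is used (protocol 8.4 specifies a mean of three for blood pressure, but the visible text has no such rule for ECGs) and that baseline follows protocol section 12, the last assessment before first dose. If the notable QTcF limit is also tabulated, use at least 450/460 ms as in Appendix 16.1. A 480 ms cut is not needed: in section 6.5.1.2 that value only marks when increased cardiac monitoring can end.

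Separately, the sponsor must reconcile protocol 9.1.1, which requires permanent discontinuation for a confirmed creatinine rise of at least 50%, with Table 16-3, which for a 50% rise asks that interruption or discontinuation be considered. The count is needed either way.

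The cost is SAP wording and two or three tables from data already collected. The downside is small counts that need cautious reading.

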# End of study (EOS) visit (Day 91)

Approximately one week after completion of the treatment period, subjects will be invited to the center for end of study (EOS) assessments.

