# Safety follow-up call (Day 114)

A follow-up telephone call for safety assessment will occur upon study visit completion (EOS) 30 days after last study dose administration. The safety follow-up includes adverse events safety monitoring.

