# 9.2 Study completion and post-study treatment

Study completion is defined as when the last subject finishes their end of study (EOS) completion visit and any repeat assessments associated with this visit have been documented and followed-up appropriately by the Investigator or, in the event of an early study termination decision, the date of that decision (e.g. each subject will be required to complete the study in its entirety and thereafter no further study treatment will be made available to them).

Upon completion of a subject's participation in the study, he/she should be treated according to his/her individual needs. It is not planned to provide QBW251 to study participants after the study is completed due to the early stage of development. Since this study is a Phase 2 study. the safety profile of the drug has not yet been established to the extent considered adequate for a provision of OBW251 with less stringent safety monitoring.

Randomized and/or treated subjects will have a safety follow-up call conducted 30 days after last administration of study treatment. The information collected is kept as source documentation. All SAEs reported during this time period must be reported as described in Section 10.1.3 and in the SOM. Documentation of attempts to contact the subject should be recorded in the source documentation.

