# 10.1.3 SAE reporting

To ensure subject safety, every SAE, regardless of causality, occurring after the subject has provided informed consent and until 30 days after the last study visit must be reported to Novartis within 24 hours of learning of its occurrence as described below. Any SAEs experienced after this period should only be reported to Novartis if the investigator suspects a causal relationship to study treatment.

**Screen Failures:** If a subject fails screening (e.g. a subject who is screened but is not treated or randomized), SAEs occurring after the subject has provided informed consent until the time the subject is deemed a Screen Failure must be reported to Novartis.

Randomized Subjects who discontinue prematurely: SAEs collected between the time a subject signs the ICF until 30 days after the subject discontinued or stopped study treatment, or had their last study visit, which ever is later should be reported to Novartis/sponsor safety within 24 hours of learning of its occurrence.

All follow-up information for the SAE including information on complications, progression of the initial SAE and recurrent episodes must be reported as follow-up to the original episode immediately, without undue delay, and under no circumstances later than 24 hours of the investigator receiving the follow-up information. An SAE occurring at a different time interval or otherwise considered completely unrelated to a previously reported one must be reported separately as a new event.

If the SAE is not previously documented in the Investigator's Brochure or Package Insert (new occurrence) and is thought to be related to the study treatment, a Novartis Chief Medical Office and subject Safety (CMO&PS) Department associate may urgently require further information from the investigator for health authority reporting. Novartis may need to issue an Investigator Notification (IN) to inform all investigators involved in any study with the same study treatment that this SAE has been reported.

Suspected Unexpected Serious Adverse Reactions (SUSARs) will be collected and reported to the competent authorities and relevant ethics committees in accordance with EU Guidance 2011/C 172/01 or as per national regulatory requirements in participating countries.

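### Safety tables stop 7 days after the last dose, on the nominal day of the only post-treatment clinic visit, so the booking day decides whether that visit's results are summarised

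*SAP*

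**What the plan says.** SAP Section 7: "Safety summaries (tables, figures) include only data from the on-treatment period with the exception of baseline data". The only other exception is a separate summary of deaths, which covers on-treatment and post-treatment deaths. SAP 7.2 defines the period as running from the first dose "to 1 week after the last actual administration of any study treatment". Protocol 12.5.2 states both rules in the same terms. AE tables count only events that start within the period, and laboratory shift tables compare baseline with the worst on-treatment value.

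Dosing runs from Day 1 through Day 84 (protocol 6.1.3). On the visit that follows, protocol 3.1 says: "Approximately one week after completion of the treatment period, subjects will be invited to the center for end of study (EOS) assessments". Table 8-1 gives it as Day 91 ±3, with vital signs, ECG, haematology and chemistry. No later clinic visit is scheduled.

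AE monitoring continues for at least 30 days after the last dose (protocol 10.1.1). The safety call is timed "30 days after last study dose administration" (protocol 3.1), Day 114 ±3 in Table 8-1. SAEs occurring after consent and "until 30 days after the last study visit must be reported" to the sponsor (protocol 10.1.3).

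**The concern.** The end of the on-treatment period and the nominal EOS day coincide. The visit has a ±3-day window and the cut-off has none. Two subjects with the same last dose, both attending within window, can be treated differently: one has EOS results in the tables and the other does not, only because of the day booked. Neither document says whether day 7 itself is inside the period, so even the nominal visit is ambiguous. SAP 7.2 also promises laboratory, ECG and vital-sign statistics by visit, but gives no rule for an EOS value beyond day 7. The programmer would have to choose.

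Subjects who stop treatment permanently but stay in the study are asked to return for the scheduled assessments (protocol 9.1.1). Under the rule, nothing collected more than 7 days after their last dose is tabulated.

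Safety and tolerability is a stated secondary objective. At stake is whether the tables give a complete, reproducible view of the end of the study and of the 30 days in which adverse events are monitored.

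**Working it through.** **The plan's calendar.** 84 + 7 = Day 91 (EOS) and 84 + 30 = Day 114 (call). Both match the protocol.

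**EOS against the cut-off, last dose on Day 84.** The cut-off is 84 + 7 = Day 91 and the permitted EOS days are 88 to 94.
- Day 7 counted as on-treatment: Days 92, 93 and 94 fall outside, 3/7 = 43%.
- Day 7 not counted: Days 91 to 94 fall outside, 4/7 = 57%.

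**Letting the Week 12 visit (84 ±3) move as well, day 7 counted.** For last-dose Days 81 to 87 against EOS Days 88 to 94:

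| Last dose | Cut-off | EOS days outside |
|---|---|---|
| Day 81 | Day 88 | 6 of 7 |
| Day 84 | Day 91 | 3 of 7 |
| Day 87 | Day 94 | 0 of 7 |

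Over all 7 × 7 = 49 pairs, the gap from last dose to EOS runs from 88 − 87 = 1 to 94 − 81 = 13 days, and 21 pairs (43%) exceed 7 days.

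**Illustrative count.** Both documents expect about 84 completers. With EOS days uniform over the window and a Day 84 last dose, 84 × 3/7 = 36 completers would have EOS values outside the summaries, or 84 × 4/7 = 48 if day 7 is excluded.

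**Early stoppers.** For a last dose on Day 28, the cut-off is 28 + 7 = Day 35. The visits on Days 56, 84 and 91 all fall outside.

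**Adverse events.** Monitoring covers at least 30 days after the last dose and the AE tables cover 7. So 30 − 7 = 23 monitored days (77%) feed no AE or SAE summary table except deaths.

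**SAE window against the last planned contact.** If EOS is the last study visit, the window closes on 91 + 30 = Day 121 and the call is on Day 114, a nominal gap of 7 days. Over the permitted windows the close is Day 118 to 124 and the call Day 111 to 117, so the gap runs from 118 − 117 = 1 to 124 − 111 = 13 days. If the call, which has its own visit number in Table 8-1, counts as the last study visit, the window closes on 114 + 30 = Day 144, 30 days after the call.

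**The case against.** **Nothing is discarded.** A reader might infer that end-of-study safety data are lost. They are not. SAP 7.2 lists all laboratory, ECG and vital-sign data by subject and visit with abnormalities flagged, adds a listing of every parameter for subjects with any abnormal laboratory value, and lists all AEs, SAEs and fatal AEs. In a trial of about 100 subjects these can be read one by one. This stands and limits the point to summaries.

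**The 7-day rule has a basis.** With the half-life of 10 to 16 hours in protocol 4.2, 7 days (168 hours) is 168/16 = 10.5 to 168/10 = 16.8 half-lives. The cut-off is defensible; the fault is only that it meets a ±3-day visit. It also follows that late off-drug values do not belong in a table defined by the worst on-treatment value.

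**43% depends on assumptions.** It needs uniform visit days. The 21-of-49 version also treats EOS as independent of the last dose, although EOS is tied to the end of treatment. This stands. But if visits cluster on Day 91, the day-7 ambiguity matters more.

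**Early stoppers are partly covered.** An AE that starts on drug and leads to stopping is on-treatment by its start date, and discontinuations due to AEs have their own summary. Subjects who leave the study are to be seen as soon as possible (protocol 8). The documents give no basis for saying that those affected mostly stopped because of an event.

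**AEs and SAEs are sought to about day 30.** The call serves that purpose, and protocol 10.1.3 is a duty to report once the site learns of an event, not a promise of contact to the window's last day. Pairing a Day 87 last dose with a Day 111 call would suggest only 111 − 87 = 24 days of follow-up. But protocol 3.1 and 9.2 time the call from the last dose: 87 + 30 = Day 117, inside the window.

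**The call as source only.** Of the call, protocol 9.2 says: "The information collected is kept as source documentation". A reader might infer that AEs heard then never reach the database. That is unsafe: 9.2 requires SAEs to be reported without excluding AEs, 10.1.1 requires AE monitoring throughout, and the span of the AE row in Table 8-1 cannot be read from the extracted text.

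**Conclusion.** The point holds as a defect in how safety data are summarised. Read literally, the plan leaves in-window EOS visits on Days 92 to 94 out of the by-visit laboratory, ECG and vital-sign summaries. For a Day 84 last dose this is 3 of 7 permitted days (4 of 7 if day 7 is excluded); as a share of visits, 43% rests on uniform visit days. It also leaves out later values from subjects who stop treatment but keep attending, and AEs and SAEs starting on days 8 to 30 after the last dose. Listings and the deaths summary limit the harm. The documents do not support the stronger conclusion that these data are dropped or the events not looked for.

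The mismatch in the SAE window is real but smaller: with EOS as the last visit, only its final part, nominally 7 days, has no planned contact.

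The primary analysis is unaffected. SAP 1.4 records a decision to stop the trial before completion, so the number affected is probably below the illustrative 36 to 48.

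**What to change.** In SAP Section 7 and protocol 12.5.2:

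1. Summarise EOS/Early Termination as its own post-treatment visit in the laboratory, ECG and vital-sign tables, whatever its gap from the last dose.
2. State whether day 7 counts as on-treatment.
3. Keep the shift table on the worst on-treatment value as defined. If EOS shifts are wanted, add a separate baseline-to-EOS shift table.
4. Add one table of AEs and SAEs with onset after the on-treatment period and up to 30 days after the last dose.

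Separately, reconcile protocol 10.1.3 (SAEs, counted from the last study visit) with 3.1, 9.2, 10.1.1 and Table 8-1 (AEs and the call, counted from the last dose), and say whether the call counts as a study visit.

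The cost is SAP and protocol wording and one or two extra tables. The summary changes need no new assessments and can be made by SAP amendment before database lock.
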